#### Paper-based approach

1. The informed consent document is delivered to the patient or LAR.
  - a) If the patient or LAR is on-site, the informed consent document may be delivered to the patient or LAR either by research staff or by clinical staff
  - b) If the LAR is off-site, the informed consent document may be emailed, faxed, or otherwise electronically transferred to the LAR (method dictated by institutional policy)
2. Research staff discuss the informed consent document with the patient or LAR either in- person or by telephone or videophone. *This step confirms subject/LAR identity.*
3. If the patient or LAR decides to consent to participate, the patient or LAR signs the paper copy of the informed consent document.
4. A photograph is taken of the signature page of the informed consent document and uploaded into the electronic database (e.g. REDCap).
  - a) If using the patient’s device (such as a patient’s personal cellular phone), a survey link can be sent to their device to allow direct upload of the image into the electronic database (e.g. REDCap).
  - b) If using a staff device, it must be approved to store PHI by the local institution. In that case, research personnel can take a photograph of the signature page of the informed consent document either directly or through the window or glass door leading into the patient’s room. The photograph can then be uploaded into the electronic database. If a staff device is taken into the patient’s room to take a photograph it must be able to be disinfected according to local institutional practices.
5. Research staff and witness provide signatures within the electronic database (e.g. REDCap) confirming their participation in the informed consent process.
6. The patient or LAR retains the paper consent document. The image of the signature page may be printed and bundled with a copy of the blank informed consent document for research records.

#### Electronic / e-consent approach

1. The electronic informed consent document is opened on a research device or a link for the electronic informed consent document is sent to the patient’s or LAR’s device.
2. Research staff discuss the informed consent document with the patient or LAR either in person or by telephone or videophone. *This step confirms subject/LAR identity.*
3. If the patient or LAR decides to consent to participate, the patient or LAR signs the electronic informed consent document. This signature may be either:
  - a) an actual signature (often tracing a finger on the screen) OR
  - b) a username and password specific to the individual signing
4. Research staff and witness provide signatures within the electronic database (e.g., REDCap) confirming their participation in the informed consent process.
5. The image of the signature page may be printed and bundled with a copy of the blank informed consent document for research records.
6. If a hospital device is provided to facilitate electronic or paper-based consent, that device will be disinfected according to institutional protocols and removed by research staff or clinical staff during the next entry into the patient’s room.

This approach complies with relevant regulations and sub-regulator guidance at 45 CFR 46.117, 45 CFR 164.512, 21 CFR 11 Subpart C (11.100–11.300), <https://www.hhs.gov/ohrp/regulations-and>

Pro00106306: Addressing psychological distress symptoms among serious illness survivors of a viral pandemic with a completely self-directed, symptom-responsive mobile mindfulness intervention

[policy/guidance/use-electronic-informed-consent-questions-and-answers/index.html](https://www.fda.gov/regulatory-information/search-fda-guidance-documents/informed-consent),  
<https://www.fda.gov/regulatory-information/search-fda-guidance-documents/informed-consent>

#### Post-hospital procedures

Patients who provided informed consent during hospitalization will be asked to confirm their interest in participation verbally during follow up calls. Patients selected for participation in post- hospital surveys who were unable to provide informed consent (enrolled via surrogate consent and unable to engage in informed consent before hospital discharge) will participate in the informed consent process by telephone. Those agreeing will provide verbal consent. The same process will be used for family members selected to participate in post-hospital procedures.

### **6.b. LIFT COVID RCT**

#### Screening

1. At the time of the 1 month (T1) BLUE CORAL post-discharge interview, the FUNCTION staff will conduct the PHQ-9 survey.
2. For those with a PHQ-9 score  $\geq 5$ , the research staff will discuss the informed consent document with the patient by telephone or videophone.

#### Informed consent

##### Verbal process

1. During the phone call, a formal DUHS Central IRB-approved telephone script for informed consent will be followed for LIFT COVID by the FUNCTION staff.
2. If the patient decides to consent to participate, the study team will record the participant's name, their contact information, and the date and time of consent. This information will be entered in the study data system.
3. If the patient requests to be called back at a different time to discuss consent, a study team member will do so. Per the patient's direction, the study team will follow the protocol for either the verbal process above or the electronic consent process described below.
4. If the patient declines, this will be noted in the study database.

##### Electronic consent process

1. For those who prefer completing electronic informed consent, they will do so by following a unique URL sent via an email to a study-specific REDCap e-consent form. Their signature will be done by tracing their finger on the screen. The e-consent form will be retained in the research data system.
2. Research staff and witness provide signatures within the electronic database confirming their participation in the informed consent process per Duke policy.
3. A copy of the signed/dated consent form will be provided to the participant.

There may be instances related to obtaining informed consent that the FUNCTION staff is unable to complete the outlined processes above. Should this occur, the FUNCTION staff will communicate with sister sites, Oregon Health & Sciences University (OHSU) and University of Colorado-Denver (UCD). OHSU and UCD may be asked to complete the recruitment and informed consent process, as well as initiate app registration as further outlined in the sections below.

## **7. Data Collection**

### **7.a. BLUE CORAL data collection**

BLUE CORAL includes data collection from enrolled patients' clinical records. There are three types of forms for each study: admission (hospital / study day 1), daily, and discharge.

The case report form (CRF) is built in REDcap which can be imported as a local instance or centrally through the PETAL CCC. Since there may be times when study personnel are mandated to work from

home due to the ongoing pandemic, BLUE CORAL has many study procedures that are designed to allow off-site completion. All elements that contribute to the COVID ordinal outcome scale are included in daily and summative data collection. Manual data entry of all elements into REDCap may not be required depending on the site's ability to extract data from the EMR.

The BLUE CORAL study will obtain pre-hospital information from patients or their caregivers before hospital discharge. The survey consists of questions regarding functional status and health-related quality of life. PETAL study staff members are familiar with the conduct of these surveys as they were used successfully in the ROSE RCT. With high severity of illness, infection control precautions, and absence of family visitation, we anticipate that survey completion will be difficult. Therefore, we have developed multiple approaches to survey completion (telephone, tablet computer, or email with either patients or families) and will attempt to complete as able.

BLUE CORAL patients who survive hospitalization, speak English, are domiciled, and did not have severe dementia or severe disability before hospitalization may be eligible to enter the post-hospital follow-up study (BLUE CORAL). This study will be conducted by the FUNCTION team at the University of Michigan, led by [name], using protocols developed and executed in the PETAL Network ROSE and ongoing CLOVERS studies. Sister sites, Oregon Health & Sciences University (OHSU) and University of Colorado-Denver, led by Drs. [name] and [name], respectively, may be asked to conduct the study visits as needed. Post-hospital follow-up will occur by telephone at 1, 3 and 6 months after hospital discharge (Table 1). Patients will provide consent for continued involvement at the time of the first call.

Table 1: Data collection timing and content for BLUE CORAL and LIFT RCT participants.					
	Hospital	1 month* (T1)	During intervention 	3 months* (T2)	6 months* (T3)
Contact info	X	X		X	X
PHQ-9 depression (primary outcome)		X	X	X	X
GAD-7 anxiety		X		X	X
EQ-5DL quality of life	X	X		X	X
ADL / IADL limitations	X	X		X	X
Financial strain	X	X		X	X
Cardiopulmonary symptoms		X		X	X
Cognitive function (MOCA/AD8, Hayling)		X		X	X
Rehospitalization		X		X	X

\* Timing is from the time of hospital discharge  
1 Collected via the Lift mobile app weekly  
2 These data collected only for LIFT RCT participants. This will be done via the app platform.

These post-hospital assessments will allow BLUE CORAL to measure the levels and rates of recovery on cardio-pulmonary symptoms as well as the key domains outlined in the NHLBI R24-funded “Improving Long-Term Outcomes” Program; to determine risk factors associated with poor outcomes; to assess the burden of COVID-19 recovery primary spouse or family caregiver of cohort members, stratified by whether the spouse themselves had COVID-19 or not; and to evaluate the association of the COVID-19 Outcome Score with patient- centered outcomes.

### 7.b. LIFT COVID Surveys

As shown in Table 1, participants enrolled in the LIFT COVID intervention arm will also complete the PHQ-9 survey weekly within the LIFT mobile app for the duration of the 4-week intervention.

### 7.c. List of all BLUE CORAL and LIFT COVID surveys

#### Inpatient

- Recent living status (1 item)
- Days hospitalized in month prior to COVID-19 admit (1 item)
- EQ-5D-5L baseline (5 items)
- Activities of Daily Living (ADLs) and Instrumental ADLs baseline (13 items)
- AD8 (8 items, completed by caregiver)
- Household Financial Strain (7 items)
- Occupation and Industry (2 items)
- Number of People in Household (1 item)

#### Post-hospital patient surveys

[figure not shown]
- COVID-19 Recovery (1 item)
- EQ-5D-5L (5 items)
- Activities of Daily Living (ADLs) and Instrumental ADLs (13 items)
- Financial Toxicity (12 items)
- Cardiopulmonary symptoms and respiratory support (13 items)
- Patient Health Questionnaire-9 (9 items)
- Generalized Anxiety Disorder-7 (7 items)
- Healthcare utilization (1 item)
- Demographics (2 items)
- Montreal Cognitive Assessment MOCA-Blind
- Hayling Test of Executive Function
- Select Current Medications, matched to those collected in-hospital

## 8. Randomization.

Figure 1 shows the general approach to screening, informed consent, and randomization. PETAL sites will obtain informed consent for the BLUE CORAL observational study. At the time of the 1-month post-discharge follow up call from the University of Michigan, potential participants will be first screened on the for sufficient distress (i.e., PHQ-9  $\geq 5$ ). For those who meet the cutoff, the staff will describe the LIFT trial and obtain informed consent by phone. For those who provide informed consent, the delegated study staff will enter the data required for randomization (contact information, stratification variable data) into the Shibboleth password-protected Lift app platform study staff dashboard. This will enable auto-randomization by the LIFT platform. Randomization will be stratified by age, gender, and baseline PHQ-9 score.

At this point, an automated SMS text message and/or email (per user preference) will be sent to the participant that alert them to their treatment group. For intervention group participants, it will also provide a link to download the LIFT app platform and a unique ID code to activate it. After download

Figure 1. Screening, consent, and randomization for the LIFT COVID RCT

**Step 1: screening by PETAL / FUNCTION.** The PHQ-9 will be administered by the University of Michigan FUNCTION staff by phone 1 month post-discharge for BLUE CORAL observational study. This will be the baseline (T1) data collection for LIFT.

**Step 2a: consent from PETAL / FUNCTION.** If PHQ-9 eligibility cutoff met, University of Michigan FUNCTION staff obtains informed consent during the phone call.

**Step 2b: consent from Duke center if needed.** If potential participant wishes to think about it, contact data passed to the LIFT sites for either follow up phone call or email-/text-based approach. If participant agrees, LIFT team then sends email and/or text. Participant clicks link in email / text to download the mobile app platform.

**Step 3: randomization.** University of Michigan or LIFT teams add contact data and key variables required for stratification for consented participant to Lift mobile app platform dashboard. The LIFT platform then automatically randomizes the participant into one of the two LIFT COVID groups (LIFT app vs. traditional care control).

**Step 4: intervention.** Intervention participants receive Lift app access. After T3 (6 month post-discharge) BLUE CORAL survey, traditional care control participants can access Lift if they wish via an email automatically sent from the LIFT platform.

Pro00106306: Addressing psychological distress symptoms among serious illness survivors of a viral pandemic with a completely self-directed, symptom-responsive mobile mindfulness intervention

and activation with the unique ID, the participant's experience will be automated.

## **9. LIFT COVID RCT procedures**

### ***Aims 1 and 2.***

LIFT is a self-directed mobile app platform based on a solid conceptual model that guides participants through a 1-month program. LIFT content includes 4 weekly app-based sessions as previously tested in a pilot RCT (NCT02701361). Each session is composed of three parts: 1. Video presentation describing rationale (3-5 min.), 2. Audio guided meditation (8-10 min.), and 3. Other relevant in-app exercises (e.g., tips to help apply mindfulness to daily life). Each week a participant completes the PHQ-9 depression symptom survey within the app. While the parent U01 factorial trial is comparing 8 versions of LIFT that differ on 3 factors (NCT04038567), the LIFT COVID RCT will use the version of LIFT that includes no introduction call, app-based response to symptoms changes during the intervention period, and standard dose. The app-based approach to non-responders, defined as those whose PHQ-9 score has increased in comparison to the previous week or whose PHQ-9 score is  $\geq 20$ , uses the app's logic to display hovering messages and notifications within the app that may be applicable to the user. Depending on whether emotional or somatic depression symptoms are dominating the PHQ-9 score for the individual, a unique video is shown within the app that features the study interventionists leading a brief exercise in which the participant is coached by the interventionist in the application of mindfulness for the symptoms the participant has endorsed. The app-based approach to non-responders has 8 unique videos, 2 for each week (i.e., one tailored to emotional symptoms, one tailored to somatic symptoms).

### ***Aim 3 procedures (cross-sectional focus groups)***

The goal of Aim 3 is to understand the barriers and facilitators to the successful use of the LIFT app from a patient's perspective within the context of a pandemic. We will use a stratified purposive design to sample 25 participants (~2 / mo.), a number sufficient for theme saturation, after 3 months post-discharge. The procedures will include a ~30-minute semi-structured one-on-one interview conducted by phone (based on participant preference and availability) by an experienced coordinator that will explore app access, use, and content. Theoretical sampling will ensure sufficient variability in characteristics that may influence experiences, stratifying cases by response to LIFT (high vs. low), LIFT use (high vs. low), demographics (age, gender), and baseline distress (moderate vs. high).

## **10. Statistical design, analyses, sample size, and power:**

### ***Aims 1 and 2***

The goal of the parent U01 trial analysis is to determine which LIFT components (i.e., factors) have the greatest salutary effects on MOST optimization criteria of feasibility, usability, and clinical impact.

Analyses for the LIFT COVID RCT's Aims 1 and 2 are designed to compare the clinical impact on psychological distress symptoms (depression, anxiety, PTSD) LIFT (n=150) vs. control (n=150) among COVID-19 patients. All participants will be analyzed by their assigned group, regardless of adherence or crossover status. Briefly, we will test the primary study hypothesis that the PHQ-9 score is lower (i.e., fewer depression symptoms) for LIFT recipients compared to control 3 months post-discharge with a general linear model using SAS PROC MIXED (SAS Institute, Cary NC). An unstructured covariance matrix will be specified to account for the correlation between longitudinal repeated measures. Similar analyses will be performed in Aim 2 for the GAD-7 and PTSS, as well as for all other outcomes at 3 and 6 months. Procedures for missing data will include (as needed) sensitivity analyses, multiple imputation PROC MI, and estimates combined using Rubin's rules as implemented in PROC MIANALYZE.

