## 5. Previous enrollment in BLUE CORAL

### **4.b. LIFT COVID eligibility**

There will be 300 BLUE CORAL patients selected for detailed post-hospital assessment—these will be the target population for the LIFT COVID RCT. If there are more eligible patients, patients may be selected randomly or according to enrichment strategies which will be informed by the composition of the cohort. Informed consent will be obtained by telephone for these potential participants.

Inclusion criteria:

1. Enrolled in BLUE CORAL
2. Survival to hospital discharge
2. English-speaking
3. Domiciled with access to a working telephone and smartphone, tablet, or computer with wifi or internet connection
4. Absence of severe dementia or severe functional disability before hospitalization or at time of 1 month post-discharge interview

Exclusion criteria:

1. PHQ-9 <5 at time of interview 1 month post-discharge
2. Suicidal ideation at time of interview 1 month post-discharge

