### ***Sample size and power considerations***

For Supplement Aim 1, we will randomize 300 patients. Even with a 40% dropout rate (i.e., 180 at 3 months) and conservative assumptions (SD=6.0,  $p=0.5$ , two-sided test, type-I error of 5%), this sample size will provide a power of 80% to detect a differential between-group PHQ-9 improvement at 3 months as small as 2.5 units, substantially less than the minimal clinically important difference (MCID) of 5.0 units. Calculations were based on mixed-models tests for a difference in slopes using PASS 16 Software (v16.0.5; Kaysville UT).

**11. Subject Participation Duration:** It will require 5 months for participants to complete the entire study from the time of randomization, including the month-long intervention and follow up surveys.

**12. Study Duration:** We estimate that from the time the RCT opens to enrollment it will require 1 year to complete all study activities.

**13. Costs to the Subject:** There are no costs to participants.

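### The primary mixed model names none of the stratification factors and no common T1 mean; adjusting for T1 PHQ-9 would raise power from about 84% to about 89-90% if separate T1 means are meant (r = 0.5), and the stated 80% is met either way

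*Combined protocol and SAP*

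**What the plan says.** Section 8 states: "Randomization will be stratified by age, gender, and baseline PHQ-9 score". Step 1 of Figure 1 says of the 1-month telephone PHQ-9: "This will be the baseline (T1) data collection for LIFT". T1 PHQ-9 is therefore known for every participant before allocation.

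Section 10 (Aims 1 and 2) holds the only description of the primary analysis. The hypothesis is that "the PHQ-9 score is lower (i.e., fewer depression symptoms) for LIFT recipients compared to control 3 months post-discharge with a general linear model", run in PROC MIXED. It adds: "An unstructured covariance matrix will be specified to account for the correlation between longitudinal repeated measures". On the analysis population: "All participants will be analyzed by their assigned group, regardless of adherence or crossover status". No fixed effects are listed, and no other section lists them.

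Under Sample size and power considerations, with 300 randomised, 180 observed at 3 months, SD 6.0, p=0.5 (undefined) and a two-sided 5% test, the plan says "this sample size will provide a power of 80% to detect a differential between-group PHQ-9 improvement at 3 months as small as 2.5 units". The basis given is: "Calculations were based on mixed-models tests for a difference in slopes using PASS 16 Software".

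**The concern.** When randomisation is stratified on a prognostic variable, the analysis would normally include that variable. Otherwise the model-based standard error ignores the balance that stratification produced and tends to be too large. Baseline PHQ-9 is also the same scale as the primary outcome, so it is likely to be its best available predictor.

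Having T1 in the response vector does not settle this. If each arm has its own T1 mean, chance T1 imbalance stays in the T2 contrast and also, with a different weight, in the change-from-T1 contrast. A T1 covariate, or one T1 mean shared by the arms, removes it. The plan states neither.

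The target contrast is also unsettled. Section 10 tests whether the 3-month score is lower, while the power statement concerns improvement through a difference in slopes. With separate T1 means these are two different estimates with different power unless the correlation is 0.5. With T1 as a covariate the treatment coefficient is the same for both.

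At stake are precision and a fully specified primary model. Bias and false-positive risk are not at issue.

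**Working it through.** Inputs from Section 10: 150 per arm randomised, 90 per arm at T2 (40% dropout), SD 6.0, difference 2.5, two-sided 5%. Assumptions: p=0.5 is the within-person correlation r; SD is 6 at each visit; dropout is at random; power uses the normal approximation, Φ(2.5/SE − 1.96).

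**1. The plan's own figure.** A two-group comparison at T2 alone has variance 2 × 36/90 = 0.80 and SE 0.894. Power is Φ(2.795 − 1.96) = 79.8%. At r = 0.5 the SD of change is 6 × √(2 × 0.5) = 6.0, so a completers' change or two-visit slope test gives the same result. The stated 80% reproduces, which supports reading p as the correlation.

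**2. Repeated-measures model with separate T1 means** (150 per arm contribute T1, 90 contribute T2):
- T2 contrast: 72 × [(1 − r²)/90 + r²/150]. At r = 0.5: 72 × [0.75/90 + 0.25/150] = 0.72, SE 0.849, power 83.8%.
- Change contrast: 72 × [(1 − r²)/90 + (1 − r)²/150]. At r = 0.5 this is also 0.72, power 83.8%.

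**3. T1 as covariate, or a common T1 mean:** 72 × (1 − r²)/90. At r = 0.5: 72 × 0.75/90 = 0.60, SE 0.775, power 89.8%.

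The 95% half-width falls from 1.96 × 0.849 = 1.66 to 1.96 × 0.775 = 1.52, about 9%.

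**4. Dependence on r** (SD held at 6; SE, power):

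| r | T2, separate T1 means | Change, separate T1 means | Adjusted or common T1 mean |
|---|---|---|---|
| 0.2 | 0.887, 80.4% | 1.037, 67.4% | 0.876, 81.4% |
| 0.3 | 0.878, 81.2% | 0.981, 72.2% | 0.853, 83.4% |
| 0.4 | 0.865, 82.4% | 0.919, 77.6% | 0.820, 86.2% |
| 0.5 | 0.849, 83.8% | 0.849, 83.8% | 0.775, 89.8% |
| 0.7 | 0.802, 87.6% | 0.672, 96.1% | 0.639, 97.5% |

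The T2 contrast gains only about 1-2 points at r = 0.2-0.3, and the change contrast only about 1-2 points at r = 0.7.

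**5. Effect of stratified allocation.** The plan gives no PHQ-9 cut-points or block size, so this step assumes two or three equal strata and permuted blocks of 4 (12,000 simulated trials per setting, r = 0.5).
- Power: 84.5% (T2) and 84.4% (change) unadjusted against 89.1% adjusted with two strata; 84.7% and 84.8% against 89.4% with three.
- T2 contrast, true against reported SE without adjustment: 0.808 against 0.850 (two strata), 0.791 against 0.851 (three). Across both contrasts the reported SE is about 5-8% too large, and type I error is 3.2-4.1%.
- With adjustment the true SE is 0.781 and 0.774, against 0.776 reported in both cases. The true variance therefore falls only 1 − (0.781/0.808)² ≈ 7% or 1 − (0.774/0.791)² ≈ 4%. The rest of the narrowing corrects a conservative reported SE.

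**The case against.** **The planned model may already be efficient.** Section 10 is a brief description and lists no fixed effects. If the T1 means are constrained equal, steps 2 and 3 coincide and nothing is lost from baseline PHQ-9. This stands. A reader might infer that the planned model definitely loses about 5 points, but the documents support only that it does so if separate T1 means are meant. That is a reason to state the model.

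**The trial meets its target without adjustment.** This also stands on the plan's inputs. At the plan's own minimal clinically important difference of 5.0 units, power exceeds 99.9% with or without adjustment (5.0/0.849 = 5.89). The 40% dropout is offered as a conservative case, so a reader should not take it as expected attrition. At 20% dropout (120 per arm) and r = 0.5, the separate-means variance is 72 × [0.75/120 + 0.25/150] = 0.57, SE 0.755, power about 91%.

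**Low correlation.** A reader might infer from the exclusion of "PHQ-9 <5 at time of interview 1 month post-discharge" that r falls to about 0.3 and that power for change falls to the 72% in the table. The documents do not support this. Truncating T1 lowers r because it shrinks the T1 SD; the slope of T2 on T1 and the residual variance stay the same, whereas the table holds SD at 6. Take normal scores with SD 6 and slope 0.5 before screening, an assumed unscreened mean of 5-12, and a cut at 5. The T1 SD becomes 3.6-4.9 and r 0.33-0.43. The variance of either contrast is 2 × [27/90 + 0.25 × (T1 SD)²/150], so power rises to about 86-88%, while the adjusted figure stays at 89.8%. The gain shrinks to about 2-4 points. If SD 6 and p=0.5 already describe enrolled patients, the entry rule is already counted.

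**The stratification figures rest on assumed strata.** They do. Only their direction, a conservative unadjusted SE, should be relied on.

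**Conclusion.** The point holds as a free improvement in precision and specification. The primary model leaves out the three variables on which allocation is stratified and does not say how T1 is handled. If separate T1 means are meant, with SD 6, r = 0.5 and 90 per arm at T2, adjusting for T1 PHQ-9 moves power for 2.5 units from about 84% to about 89-90%. That is a gain of about 4-6 points, of which part corrects an over-wide interval when allocation is stratified.

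The size depends on r, on the contrast and on reading p=0.5 as the correlation. No gain can be computed for age or gender, because the documents give no figure for how strongly either predicts PHQ-9.

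A reader might go further and conclude that the analysis is biased, that it inflates type I error or that the trial is underpowered. None of these follows: randomisation protects the unadjusted contrast, the error from ignoring strata is conservative, and the stated 80% reproduces.

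**What to change.** Write the primary model out in Section 10:
- T2 and T3 PHQ-9 as the response, with treatment, visit, treatment-by-visit, continuous T1 PHQ-9 and its visit interaction, age and gender. Alternatively, keep T1 in the response with one T1 mean common to both arms, plus age and gender.
- Name the LIFT minus control difference at T2 as the primary estimate, and bring the power statement into line with it.
- Define p in the power statement.
- Use the same form for secondary outcomes that have a T1 value, such as GAD-7.

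The cost is SAP wording only. T1 PHQ-9 is recorded at screening and the stratification data are entered before allocation, so no extra data or participants are needed. The text should be fixed before any outcome comparison by arm.
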